5.3 BIOMARKER AND RESEARCH METHODS

The technology platforms that are able to interrogate genomic structure and function are constantly in flux; therefore, the exact nature of the methodologies that will be employed will be assessed at the time that the samples are ready for analysis. The protocol will be amended at that time, if needed, to described the intended techniques prior to initiating the analyses.

The following are technologies that are currently in use for each planned analysis:

5.3.1 Molecular Profiling

Immunohistochemical (IHC) analyses, including FISH and/or PCR testing, will take part in tumor tissue samples, including but not necessarily limited to CD3, CD4, CD5, CD8, CD14, CD16, CD19, CD20, CD22, CD23, CD25, CD38, CD45RA, CD45RO, CD56, CD62L, CD69, CD79a/CD79b, CD122, and NKG2D.

5.3.2 Immune Subset Analysis

Peripheral blood mononuclear cells (PBMC) will be assessed using multiparameter flow cytometry for immune subsets including but not necessarily limited to CD8+ T-cells, CD4+Foxp3- T-cells, Tregs, T_{ex} , Th1, Th2 and Th17+ CD4+ T-cells, NK cells and subsets, monocyte subsets, MDSC subsets. Assessment may include functional markers, i.e. PD-1, Tim-3, CTLA-4, PD-L1, HLA-DR, Ki67 and/or CD40.

5.3.3 ADCC Analysis

Peripheral blood mononuclear cells (PBMCs) should be isolated by Ficoll-Hypaque Density Gradient Centrifugation. The viable cells should be viably frozen and stored in liquid nitrogen. The ADCC assay will be performed on the same occasion for all samples of a given patient. Vials of frozen cells will be thawed using standard procedures 18 hours before the assay in accord with our experience with normal donors. 1.5 million of patient's PBMCs obtained before and on day 15 following IL-15 injection will be tested in aliquots as follows:

- Tested alone
- Tested with untreated Raji cells and with Raji cells coated with an antibody to CD20 for 5 hours
- In addition, we may utilize an ATL cell line in addition to Raji cells. These cell populations will be stained with CD107, CD3, CD56, and CD94.

5.3.4 cfDNA/ctDNA

Since the methods of molecular monitoring in the peripheral blood is an emerging field with numerous technologies under development, the storage of peripheral blood mononuclear cells (PBMC), serum, and plasma will all be performed allowing for future comparison of the different

Version Date: 09/14/2021

compartments for analytes that include cell-free circulating tumor DNA (ctDNA), and RNA sequencing of circulating tumor cells. Studies to be performed on these samples include: cfDNA/ctDNA for liquid genotyping as a non-invasive dynamic monitoring of disease as well as monitoring for individual molecular aberrations that herald progression or disease transformation; specifically, amplification and sequencing of the VDJ segment of the immunoglobulin receptor is planned. Germline DNA obtained from saliva, blood, or buccal mucosa will be used to discriminate somatic from germline mutations during cfDNA and ctDNA analyses.

5.3.5 DNA/RNA Sequencing

Genomic DNA and total RNA will be extracted from tumor samples using a Qiagen All-prep kit. For individual target genes that are recurrently mutated in CLL, classical Sanger sequencing will be performed on PCR amplicons, using primers surrounding the known sites of mutation. To broadly assess mutations, next generation sequencing (e.g., on an Illumina HiSeq 2000 platform) will be employed, using a paired end sequencing strategy of libraries constructed from tumor DNA. DNA will either be sequenced in its entirety from a whole genome library or will be first enriched for exonic sequences using the Agilent Sure Select system, aiming for 30X or 100X average coverage per base, respectively. The sequence fragments will be mapped back to the genome using the BWA algorithm. Of sequences overlapping a particular base pair in the genome, the percent mutant calls greater that 20% with a minimum of 25X coverage will be considered as an arbitrary threshold for single nucleotide variants (SNVs). SNVs that are not present in the matched normal sample will be considered candidate somatic mutations.

A related technology, RNA-Seq, utilizes RNA from the tumor specimen to create a cDNA library for high-throughput sequencing. RNA-seq will be performed using Illumina kits followed by high-throughput sequencing on an Illumina HighSeq 2000 machine. The cutoffs for coverage and percent mutant calls mentioned above will also be used to identify putative SNVs. RNA sequencing will also be used to read out digital gene expression across the genome as described.

Recent advances in genomic technologies enable GEP at the single cell level, a distinct advantage over conventional GEP which cannot always distinguish tumor vs non-tumor gene expression. Single-cell approaches allow identification of the evolution of rare populations of resistant tumor cells, as well as identification of TME cells critical for the survival of the tumor. The Center for Cancer Research (CCR) has recently opened a single cell analysis core facility with expert staff headed by [name] within the CCR Genomics Core. This facility has the ability to take purified viably frozen cells banked from patient biopsies and prepare them, using well-validated 10X Genomics technology, for single-cell RNA sequencing. This core is directly integrated with the NCI Sequencing core facility to provide high-quality, deep-sequencing of the single cell RNA-SEQ samples, as well as 'first-pass' data processing and analysis. Data will then be transferred to lymphoma researchers and bio-informaticians in the [name] lab for further analysis of gene expression patterns and cellular population dynamics.

5.3.6 Other Analyses

Other analyses include the following:

- Cell analysis and histological (e.g., H&E), immunohistochemical review and analysis per standard and established research techniques (e.g., PD-1/PD-L1 expression [Dako], FISH for del(17p), and other IHC analyses in blood and tissue).
- Cytokine analysis (e.g., IL-6, IL-10, interferon beta, TNF-alpha)

Version Date: 09/14/2021

5.3.7 Future Use

Any blood, tissue, or other products or portions leftover from other analyses will be stored for future research.

5.4 SAMPLE STORAGE, TRACKING AND DISPOSITION

5.4.1 General

Samples will be ordered in CRIS and tracked through a Clinical Trial Data Management system. Should a CRIS screen not be available, the CRIS downtime procedures will be followed. Samples will not be sent outside NIH without appropriate approvals and/ or agreements, if required.

All specimens obtained in the protocol are used as defined in the protocol. Any specimens that are remaining at the completion of the protocol will be stored in the conditions described below. The study will remain open so long as sample or data analysis continues. Samples from consenting patients will be stored until they are no longer of scientific value or if a subject withdraws consent for their continued use, at which time they will be destroyed.

If the patient withdraws consent his/her data will be excluded from future distributions, but data that have already been distributed for approved research use will not be able to be retrieved.

The PI will record any loss or unanticipated destruction of samples as a deviation. Reporting will be per the requirements in section 7.2.1.

5.4.2 Lymphoid Malignancies Branch – [name] Laboratory

Under the direction of [name], all samples processed by the laboratory will be uniquely barcoded, with data entered using a secure computerized database and backup hardcopy process per standard laboratory practice.

Samples are stored in labeled boxes in secured freezers (i.e., -20°C to -80°C, or other, as appropriate) according to stability requirements; these freezers are located onsite. Access to stored clinical samples is restricted and limited to research personnel for approved analyses only (as per the IRB approved protocol).

Upon completion of planned analyses by the [name] lab, leftover samples may be stored for future analyses at the Clinical Support Laboratory, Leidos Biomedical Research, Inc.in Frederick, MD (see below).

5.4.3 Clinical Support Laboratory, Leidos Biomedical Research, Inc.in Frederick, MD

The Clinical Support Laboratory, Leidos Biomedical Research, Inc. processes and cryopreserves samples in support of IRB-approved, NCI clinical trials. The laboratory is CLIA certified for anti-IL15 and certain cytokine measurements, and all laboratory areas operate under a Quality Assurance Plan with documented Standard Operating Procedures that are reviewed annually. Laboratory personnel are assessed for competency prior to being permitted to work with patient samples. Efforts to ensure protection of patient information include:

- The laboratory is located in a controlled-access building and laboratory doors are kept locked at all times. Visitors to the laboratory are required to be accompanied by laboratory staff at all times.
- Hard copy records or electronic copies of documents containing patient information are kept in the locked laboratory or other controlled access locations.
- An electronic database is used to store information related to patient samples processed by the laboratory.

Version Date: 09/14/2021

• The database resides on a dedicated program server that is kept in a central, locked computer facility.

- The facility is supported by two IT specialists who maintain up to date security features including virus and firewall protection.
- Program access is limited to specified computers as designated by the laboratory director. Each of these computers has a password restricted login screen.
- The database sample entry program itself is accessed through a password protected entry screen.
- The database program has different levels of access approval to limit unauthorized changes to specimen records and the program maintains a sample history.
- Upon specimen receipt, each sample is assigned a unique, sequential laboratory accession ID number. All products generated by the laboratory that will be stored either in the laboratory freezers or at a central repository facility are identified by this accession ID.
- Inventory information will be stored at the vial level and each vial will be labeled with both a sample ID and a vial sequence number.
- Vial labels do not contain any personal identifier information.
- Samples are stored inventoried in locked laboratory freezers and are routinely transferred to the NCI-Frederick repository facilities for long-term storage.
- Access to stored clinical samples is restricted. Investigators establish sample collections under "Source Codes" and the investigator responsible for the collections, the protocol Principal Investigator, specifies who has access to the collection.
- Specific permissions will be required to view, input or withdraw samples from a collection. Sample withdrawal requests submitted to approved laboratory staff by anyone other than the repository source code owner are submitted to the source code owner for approval. The repository facility will also notify the Source Code holder of any submitted requests for sample withdrawal.
- It is the responsibility of the Source Code holder (the NCI Principal Investigator) to ensure that samples requested and approved for withdrawal are being used in a manner consistent with IRB approval.
- The Clinical Support Laboratory in Frederick does perform testing services that may be requested by clinical investigators including, but not limited to, immunophenotyping by flow cytometry and cytokine testing using ELISA or multiplex platforms.
- When requests are submitted by the NCI investigator for shipment of samples outside of the NIH it is the policy of the laboratory to request documentation that a Material Transfer Agreement is in place that covers the specimen transfer. The laboratory does not provide patient identifier information as part of the transfer process but may, at the discretion of the NCI investigator, group samples from individual patients when that is critical to the testing process.
- The NCI investigator responsible for the sample collection is responsible for ensuring appropriate approvals and/ or agreements are in place, if required, prior to requesting the laboratory to ship samples outside of the NIH.

5.4.4 Hematopathology Section of Laboratory of Pathology (Tissue samples)

Archival and/or freshly collected and processed tumor tissue remaining after any routine analysis and reporting may be stored in the Hematopathology Section of Laboratory of Pathology until request by the investigators for planned and/or future research assays if the patient has agreed to

Version Date: 09/14/2021

allowing specimens to be used in future research studies. IRB approval will be obtained before using any samples to conduct studies that are not described within this protocol. Samples will be stored under conditions appropriate to the type of sample and processing (e.g., ambient or frozen).

Tissue that is given to the technician will be assigned an accession number (HP#) in the HP Case Log book; sample tracking also takes place with a FileMaker Pro data base called HP Patient Information and Specimen Inventory. A Patient background sheet may be filled out and filed with any accompanying paperwork, with final reports and any supplemental reports that follow added as completed.

5.5 SAMPLES FOR GENETIC/GENOMIC ANALYSIS

5.5.1 Description of the scope of genetic/genomic analysis

The research correlates for this study are expected to include DNA/RNA sequencing of tumors, including circulating tumor (ct) DNA. In addition, whole exome sequencing may include evaluation for known lymphoma mutations. For any genetic studies performed, the results will be deposited in a database such as dbGaP per NIH requirements. Although there is controlled access to such a database, such a submission carries theoretical risks of revealing the identity of the subject. This is discussed in the consent.

5.5.2 Description of how privacy and confidentiality of medical information/biological specimens will be maximized

Confidentiality for genetic samples will be maintained as described (Section **5.4.2**). In addition, a Certificate of Confidentiality has been obtained for this study.

5.5.3 Management of Results

Subjects will be contacted if a clinically actionable gene variant is discovered. Clinically actionable findings for this study are defined as disorders appearing in the American College of Medical Genetics and Genomics recommendations for the return of incidental findings that is current at the time of primary analysis. (A list of current guidelines is maintained on the CCR intranet: https://ccrod.cancer.gov/confluence/display/CCRCRO/Incidental+Findings+Lists).

5.5.4 Genetic Counseling

Subjects will be contacted with a request to provide a blood sample to be sent to a CLIA certified laboratory. If the research findings are verified in the CLIA certified lab, the subject will be offered the opportunity to come to NIH to have genetic education and counseling to explain this result; at the time of any such event(s), these activities will be funded by the NCI/CCR in consideration of the specific circumstances. If the subject does not want to come to NIH, a referral to a local genetic healthcare provider will be provided (at their expense).

This is the only time during the course of the study that incidental findings will be returned. No interrogations regarding clinically actionable findings will be made after the primary analysis.

6 DATA COLLECTION AND EVALUATION

6.1 DATA COLLECTION

6.1.1 Summary

The PI will be responsible for overseeing entry of data into an in-house password protected electronic system (C3D) and ensuring data accuracy, consistency and timeliness. The principal investigator, associate investigators/research nurses and/or a contracted data manager will assist

Version Date: 09/14/2021

with the data management efforts. Primary and final analyzed data will have identifiers so that research data can be attributed to an individual human subject participant.

All adverse events, including clinically significant abnormal findings on laboratory evaluations, regardless of severity, will be followed until return to baseline or stabilization of event.

Document AEs from the first study intervention through 30 days after the last study intervention was administered. Beyond 30 days after the last intervention, only adverse events which are serious and related to the study intervention need to be recorded.

End of study procedures: Data will be stored according to HHS, FDA regulations, and NIH Intramural Records Retention Schedule as applicable.

Loss or destruction of data: Should we become aware that a major breach in our plan to protect subject confidentiality and trial data has occurred, this will be reported expeditiously per requirements in section 7.2.1.

6.1.2 Data Collection/Recording Exceptions

6.1.2.1 Abnormal Laboratory Values

An abnormal laboratory value will be recorded in the database as an AE **only** if the laboratory abnormality is characterized by any of the following:

- Results in discontinuation from the study
- Is associated with clinical signs or symptoms
- Requires treatment or any other therapeutic intervention
- Is associated with death or another serious adverse event, including hospitalization.
- Is judged by the Investigator to be of significant clinical impact
- If any abnormal laboratory result is considered clinically significant, the investigator will provide details about the action taken with respect to the test drug and about the patient's outcome.

6.1.2.2 Hospitalizations

Any cases of planned or prolonged hospitalization are not considered serious adverse events if for the following reasons:

- Technical, practical, or social reasons, in absence of an AE
- Routine treatment or monitoring of the studied indication not associated with any deterioration in condition, including scheduled therapy or standard procedure for the target disease of the study, and those required to allow efficacy measurement for the study
- Diagnostic or elective surgical procedures for preexisting conditions or a procedure that is planned (e.g., planned prior to starting of treatment on study)
- Closer monitoring and/or prophylaxis of TLS at any cycle
- Emergency outpatient treatment or observation that does not result in admission, unless fulfilling other seriousness criteria

Version Date: 09/14/2021

6.2 DATA SHARING PLANS

6.2.1 Human Data Sharing Plan

What data will be shared?

I will share human data generated in this research for future research as follows:

- X Coded, linked data in an NIH-funded or approved public repository.
- X Coded, linked data in another public repository
- X Coded, linked data in BTRIS (automatic for activities in the Clinical Center)

How and where will the data be shared?

Data will be shared through:

- X An NIH-funded or approved public repository. Insert name or names: ClinicalTrials.gov, dbGaP.
- X BTRIS (automatic for activities in the Clinical Center)
- X Publication and/or public presentations.

When will the data be shared?

X At the time of publication or shortly thereafter.

6.2.2 Genomic Data Sharing Plan

Unlinked genomic data will be deposited in public genomic databases such as dbGaP in compliance with the NIH Genomic Data Sharing Policy.

6.3 RESPONSE CRITERIA

Responses for spleen and lymphadenopathy will be assessed using CT scan measurements and not physical exam. Response assessments will be made by IWCLL 2018 guidelines(9). Response includes complete response (CR), and partial response (PR).

	Criteria of response								
Response	CR	PR	PD	SD					
Group A ^A									
Lymphadenopathy ^B	None >1.5cm	Decrease ≥50%	Increase ≥50% or any new lesion > 1.5cm	Change of - 49% to +49%					
Liver and/or spleen size	Spleen size <13cm; liver size normal	Decrease ≥50% (from baseline)	Increase ≥50% from baseline or from response	Change of - 49% to +49%					
Constitutional symptoms	None	Any	Any	Any					
Circulating lymphocyte count	Normal	Decrease ≥50% from baseline	Increase ≥50% over baseline ^D	Change of - 49% to +49%					
Group B ^A									
Platelet count	>100,000/ μL	>100,000/ µL or increase ≥50% over baseline	Decrease ≥50% from baseline secondary to CLL	Change of - 49% to +49%					

Version Date: 09/14/2021

Criteria of response									
Response	CR	PR	PD	SD					
Hemoglobin	>11.0 g/dL (untransfused and without erythropoietin)	>11.0 g/dL or increase ≥50% over baseline	Decrease ≥50% from baseline secondary to CLL	Increased but <11.0 g/dL or <50% over baseline, or decrease <2 g/dL					
Bone marrow ^C	Normocellular, no CLL cells, no B-lymphoid nodules.	Presence of CLL cells, or of B-lymphoid nodules, or not done	Increase of CLL cells by ≥50% on successive biopsies	No change in marrow infiltrate					

Footnotes:

CR (**complete response**): Disease-related constitutional symptoms resolved and all above criteria met, includes bone marrow biopsy

CRi (complete response with incomplete marrow recovery): CR with incomplete hematopoietic recovery **PR (partial response):** Two criteria from Group A if abnormal at baseline plus one of the criteria from Group B must be met, requires the absence of growth factor or transfusion support

SD (stable disease): Defined as not achieving CR, or PR, but not fulfilling the criteria for PD will be considered to have stable disease (which is equivalent to no response)

PD (**progressive disease**): One criteria from Group A or B are met or development of transformation to a more aggressive histology

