6.3.3 Progression-Free Survival

Progression-free survival (PFS) is defined as the duration of time from the date of study enrollment until time of disease relapse, disease progression, or death, whichever occurs first.

A Group A criteria define the tumor load. Group B criteria define the function of the hematopoietic system or marrow. For CR, all of the criteria have to be met.

^B Sum of the product (SPDs) of up to 6 lymph nodes as evaluated by CT scans. If CT is unavailable, the absence of enlarged lymph nodes (> 1.5cm) documented by physical exam is acceptable. For progression, SPDs should increase by >50% and at least one of the target lesions should be pathologically enlarged (> 1.5cm).

^C Complete response requires confirmation with bone marrow biopsy.

^D For progression, absolute lymphocyte count should increase ≥ 50% from nadir confirmed with two consecutive assessments within 3 months. CD19 B cell count should be >5,000/μL in at least one of the two assessments. Abbreviations and definitions:

Version Date: 09/14/2021

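### Read literally, the spleen criterion for partial response is stricter than the one for complete response when the baseline spleen is 13 to under 26 cm, and nothing in 6.3 says that normalisation counts toward PR

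*Combined protocol and SAP*

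**What the plan says.** The liver and spleen row of the table in 6.3 mixes two kinds of threshold:

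- CR is absolute: "Spleen size <13cm; liver size normal".
- PR is relative: "Decrease ≥50% (from baseline").
- SD is a relative band: "Change of - 49% to +49"%.

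The section also fixes the method of measurement: "Responses for spleen and lymphadenopathy will be assessed using CT scan measurements and not physical exam". It does not say whether the percentage applies to total length, to volume or to enlargement above normal. It does not say that an organ meeting the CR cell also meets the PR cell. The platelet and hemoglobin rows do give PR an absolute alternative beside the percentage; the liver and spleen row does not.

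Response is then assigned to the patient, not to the organ. For CR, footnote A to the table states: "For CR, all of the criteria have to be met". The CR definition includes a bone marrow biopsy. For PR: "Two criteria from Group A if abnormal at baseline plus one of the criteria from Group B must be met", without growth factor or transfusion support. SD is the remainder: "Defined as not achieving CR, or PR, but not fulfilling the criteria for PD will be considered to have stable disease".

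**The concern.** A criterion for partial response should be no harder to meet than the criterion for complete response on the same organ. Here the order reverses over a range of spleen sizes that the trial can expect to see, since massive, progressive or symptomatic splenomegaly is one of the alternative ways to satisfy the active-disease criterion in 2.1.1.4.

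The reversal matters for a patient who cannot be called CR for some other reason and so must be scored through the PR cells. Marrow examination after cycles 3 and 6 is optional under footnote 10 of the study calendar (3.9), yet CR requires it, so such patients are plausible. If the normalised spleen earns no PR credit, the patient may be recorded as stable disease. That removes a responder from the overall response rate (10.1) and from the duration-of-response analysis (6.3.2, 10.4.3).

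**Working it through.** The plan gives no computed figure for this point, so there is none to reproduce.

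**Inputs (6.3 table):** CR spleen size below 13 cm; PR a fall of at least 50% from baseline; SD a change from -49% to +49%. **Assumption:** size is total CT length in cm, the only unit the row gives.

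**Step 1, the row.** Let B be the baseline length.

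- PR cut-off = B/2.
- B/2 < 13 exactly when B < 26.
- Percentage fall that brings the spleen to 13 cm = 100 × (B - 13)/B. CR needs slightly more than this.

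| B (cm) | PR cut-off B/2 (cm) | Fall to reach 13 cm |
|---|---|---|
| 16 | 8.0 | 18.8% |
| 18 | 9.0 | 27.8% |
| 20 | 10.0 | 35.0% |
| 24 | 12.0 | 45.8% |
| 26 | 13.0 | 50.0% |
| 30 | 15.0 | 56.7% |

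The order is reversed for an enlarged spleen from 13 to just under 26 cm. Examples:

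- 18 to 12 cm: 6/18 = 33.3%. Meets CR, fails PR, lies in the SD band.
- 20 to 12 cm: 8/20 = 40.0%. Same result.
- 24 to 12 cm: 12/24 = 50.0%. Meets both CR and PR, so not every normalised spleen is affected.

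**Step 2, the patient.** Take a spleen that normalised with a fall of less than 50%, a Group B criterion met, no growth factor or transfusion support, no progression, and no CR or CRi. Let k be the number of other Group A criteria met. The two-criteria rule is taken as written, with no relief for a patient who had only one abnormal row.

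| k | As written | If meeting the CR cell counted as PR |
|---|---|---|
| 2 or more | PR | PR |
| 1 | SD | PR |
| 0 | SD | SD |

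Only k = 1 changes category. The PR cell for constitutional symptoms accepts any state, so a patient with symptoms at baseline may already hold one criterion. For that patient the spleen decides when neither nodes nor lymphocytes meet PR. Without baseline symptoms, it decides when exactly one of those two does.

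A concrete case: abnormal at baseline only in nodes and spleen; nodes resolve; spleen goes from 18 to 12 cm; platelets and hemoglobin are at response level; no marrow is taken. CR is barred for want of a biopsy. The spleen fails PR, one Group A criterion remains, and the patient is SD.

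**Step 3, size.** Section 10.2 gives 21 evaluable patients at most and an accrual ceiling of 24. One reclassified patient moves the response rate by 1/24 = 4.2 or 1/21 = 4.8 percentage points. With fewer patients the step is larger.

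**The case against.** The strongest reply is that the total-length reading is an assumption. The row does not define the quantity being halved, and 6.3 defers to the IWCLL guideline, which may settle it. If the 50% is applied to the excess over 13 cm, the PR cut-off becomes 13 + (B - 13)/2, for example 16.5 cm when B = 20. The reversal then disappears. This stands as a limit on the finding, but it does not remove it. The plan does not state that reading, and the pointer is itself unclear: 6.3 names the 2018 guideline but cites reference 9, which the reference list shows as the 2008 paper. Two assessors could score the same scan differently.

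A reader might also infer three stronger points, which the documents do not support:

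- *That a normalised spleen is in general scored as stable disease.* SD is a patient-level remainder. The patient may be CR or CRi, or PR through two other Group A rows. A missing marrow does not itself block PR either, since the PR marrow cell accepts that it was not done.
- *That splenic progression is delayed, because an 18 cm spleen must reach 27 cm.* The PD cell reads "Increase ≥50% from baseline or from response", and 6.3.1 and 6.3.2 take the smallest on-treatment measurement as the reference. A spleen that went from 18 to 12 cm meets the PD cell at 12 × 1.5 = 18 cm. The 27 cm figure applies only to a spleen that never shrank, and any single PD criterion is enough.
- *That one patient moves the response rate by 11 points.* That is 1/9, using only the patients at the MTD. Section 10.4.3 requires response reports to cover all patients in the study.

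**Conclusion.** The point holds in limited form. On the literal total-length reading, the spleen PR cell is stricter than the CR cell for enlarged spleens of 13 to under 26 cm at baseline, and no other part of the plan says that meeting the CR cell counts toward PR. Where this misclassifies a patient, the error lowers the response rate. It does so only in the k = 1 pattern set out above, at 4.2 to 4.8 percentage points per patient at full accrual, with loss of that patient from duration of response.

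The documents give no baseline spleen sizes, so neither the number affected nor an actual bias can be shown. The response rate is a secondary endpoint reported with a 95% confidence interval and no test. The MTD, the DLT assessment and the sample size are untouched. This should be corrected because a stated rule gives a perverse result, but it does not threaten the trial's primary purpose.

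**What to change.** In the table in 6.3:

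1. Amend the liver and spleen PR cell so that it is met either by the existing 50% fall or by meeting the CR cell of that row. This follows the pattern already used for platelets and hemoglobin.
2. State that an organ meeting the CR cell is not scored in the SD band. Say so for the liver as well, which shares the row but has no length threshold.
3. State what the percentage is measured on, consistently with the guideline the protocol adopts, and cite the edition meant.

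Rescaling PR, SD and PD to the excess over 13 cm is not needed to remove the reversal. It might depart from the adopted guideline, and it would leave the liver unaddressed.

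The cost is one table cell and two or three sentences. The CT measurements are already collected, so no new procedure or patient is needed, and any assessments already made can be re-scored from them.
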